1.3.2. Rationale for Design

This study is a Phase 1, non-randomized, open-label, single-dose, parallel-group study of PF-05221304 in subjects with varying degrees of hepatic impairment and subjects without hepatic impairment, matched for age as well as body weight (and as much as practically possible gender). Details on age- and body weight- matching criteria are specified in [Section 3.1](#). This study is proposed following a single dose of PF-05221304 considering that single dose plasma PK of PF-05221304 is generally predictive of exposure upon repeated dosing.

The current study will include subjects without hepatic impairment who have been demographically-matched to subjects with mild, moderate, and severe hepatic impairment as defined by Child-Pugh Classification (refer to [Appendix 2](#)). All subjects enrolled in this study will receive one single oral 25 mg dose of PF-05221304 in the fed state. To adequately characterize the elimination phase of the plasma PF-05221304 concentration-time profile in the cohorts with varying degrees of hepatic impairment, where the elimination half-life of PF-05221304 may be prolonged, the PK sampling will be collected serially up to 144 hours post-dose. To assess the in vivo protein binding of PF-05221304 with varying degrees of hepatic impairment, the fraction unbound (f_u) of PF-05221304 will be determined at approximately the expected time of maximum concentration (T_{max}) in each subject. CCI

[REDACTED]

In this study, PF-05221304 administration is planned to occur with the morning standard meal (refer to [Section 4.4.1](#)) to ensure consistency with the intended dosing scheme in the target patient population.

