2. STUDY OBJECTIVES AND ENDPOINTS

Primary Objective:	Primary Endpoints:
To compare the pharmacokinetics of PF-05221304 (both total and unbound) following administration of a single oral dose in adult subjects with varying degrees of hepatic impairment relative to age- and body weight-matched subjects without hepatic impairment.	PF-05221304 PK parameters derived from plasma: 
 C_{max}, AUC_{inf}, f_u, $C_{max,u}$, and $AUC_{inf,u}$.
Secondary Objectives:	Secondary Endpoints:
To compare additional pharmacokinetic parameters (both total and unbound) of PF-05221304 following administration of a single oral dose in adult subjects with varying degrees of hepatic impairment relative to age- and body weight-matched subjects without hepatic impairment.	PF-05221304 PK parameters derived from plasma: 
 T_{max}, AUC_{last}, $AUC_{last,u}$, CL/F, CL_u/F, V_z/F, $V_{z,u}/F$ and $t_{1/2}$, as data permit.
To evaluate the safety and tolerability of a single oral dose of PF-05221304 when administered to adult subjects with varying degrees of hepatic impairment relative to age- and body weight-matched subjects without hepatic impairment.	Assessment of treatment-emergent adverse events, clinical laboratory tests, vital signs, and 12-lead ECGs.

090177e190d319bb\Approved\Approved On: 29-Apr-2019 07:31 (GMT)

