9. DATA ANALYSIS/STATISTICAL METHODS

Detailed methodology for summary and statistical analyses of the data collected in this study is outlined here and further detailed in a statistical analysis plan (SAP), which will be maintained by the sponsor. The SAP may modify what is outlined in the protocol where appropriate; however, any major modifications of the primary endpoint definitions or their analyses will also be reflected in a protocol amendment.

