9.3.2. Derivation of Pharmacokinetic Parameters Prior to Analysis

The plasma PK parameters for PF-05221304 following single dose administration will be derived from the concentration-time profiles as detailed in Table 5. Actual PK sampling times will be used in the derivation of PK parameters. The fraction of PF-05221304 unbound in plasma (f_u) will be determined and reported for each subject by the analytical lab.

Table 5. Plasma PK Parameters

Parameter	Definition	Method of Determination
AUC_{last}	Area under the plasma concentration-time profile from time zero to the time of the last quantifiable concentration (C_{last})	Linear/Log trapezoidal method
$AUC_{last,u}$	Unbound area under the plasma concentration-time profile from time zero to the time of the last quantifiable concentration (C_{last})	$f_u * AUC_{last}$
AUC_{inf}^*	Area under the plasma concentration-time profile from time zero extrapolated to infinite time	$AUC_{last} + (C_{last}^*/k_{el})$, where C_{last}^* is the predicted plasma concentration at the last quantifiable time point estimated from the log-linear regression analysis
$AUC_{inf,u}^*$	Unbound area under the plasma concentration-time profile from time zero extrapolated to infinite time	$f_u * AUC_{inf}^*$
C_{max}	Maximum plasma concentration	Observed directly from data
$C_{max,u}$	Unbound maximum plasma concentration	$f_u * C_{max}$
T_{max}	Time for C_{max}	Observed directly from data as time of first occurrence
$t_{1/2}^*$	Terminal half-life	$\text{Log}_e(2)/k_{el}$, where k_{el} is the terminal phase rate constant calculated by a linear regression of the log-linear concentration-time curve. Only those data points judged to describe the terminal log-linear decline will be used in the regression.
CL/F^*	Apparent clearance	Dose/AUC_{inf}
CL_u/F^*	Unbound apparent clearance	$f_u * CL/F$
V_z/F^*	Apparent volume of distribution	$\text{Dose}/(AUC_{inf} * k_{el})$
$V_{z,u}/F^*$	Unbound apparent volume of distribution	$f_u * V_z/F$

*As data permits

For list of abbreviations refer to [Appendix 1](#)

090177e190d319bb\Approved\Approved On: 29-Apr-2019 07:31 (GMT)

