9.3.3. Statistical Methods

The effect of varying degrees of hepatic impairment on PK parameters will be assessed by constructing 90% confidence intervals around the estimated difference between each of the Test (impaired) cohorts and the Reference (without hepatic impairment) cohort using a one-way ANOVA model based on natural log transformed data.

One-way analysis of variance (ANOVA) will be used to compare the natural log transformed PF-05221304 AUC_{inf} , AUC_{last} and C_{max} , unbound AUC_{inf} ($AUC_{inf,u}$), unbound AUC_{last} ($AUC_{last,u}$), and unbound C_{max} ($C_{max,u}$), as data permit, for each of the hepatic impairment classification cohorts (Test) to the cohort without hepatic impairment (Reference). Estimates of the adjusted mean differences (Test-Reference) and corresponding 90% confidence intervals will be obtained from the model. The adjusted mean differences and 90% confidence intervals for the differences will be exponentiated to provide estimates of the ratio of adjusted geometric means (Test/Reference) and 90% confidence intervals for the ratios.

CCI

[figure not shown]
The PF-05221304 PK parameters C_{max} , AUC_{last} , AUC_{inf} , f_u , T_{max} , $t_{1/2}$, CL/F , V_z/F , $AUC_{inf,u}$, $AUC_{last,u}$, $C_{max,u}$, CL_u/F , and V_{zu}/F will be summarized descriptively by hepatic function cohort. Individual PF-05221304 concentrations will be listed and summarized descriptively by nominal PK sampling time and hepatic function cohort. Individual subject and summary profiles (median and means) of the concentration-time data will be plotted by treatment for both total plasma PF-05221304 and unbound PF-05221304. For summary statistics and summary plots by sampling time, the nominal PK sampling time will be used; for individual subject plots by time, the actual PK sampling time will be used. PF-05221304 AUC_{inf} , AUC_{last} , C_{max} , $AUC_{inf,u}$, $AUC_{last,u}$, and $C_{max,u}$ individual subject parameters will be plotted by hepatic function cohort.

Linear regression may be used to analyze the potential relationship between appropriate PK parameters (eg CL/F and V_z/F) and hepatic function (eg, serum albumin concentration, or prothrombin time). Estimates of the slope and intercept, together with their precision (90% confidence interval [CI]), and the coefficient of determination will be obtained from the model.

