6.3. Other Endpoints

6.3.1. PK Endpoints

Blood samples for PK analysis of PF-05221304 will be taken according to the Schedule of Activities given in the protocol.

The following PK parameters will be calculated for PF-05221304 (if possible) from the concentration-time data using standard non-compartmental methods:

Table 3. Noncompartmental PK Parameters

PK Parameter	Analysis Scale	PF-05221304	Definition
AUC_{last}	ln	A, D	Area under the plasma concentration-time profile from time zero to the time of the last quantifiable concentration (C_{last})
$AUC_{last,u}$	ln	A, D	Unbound area under the plasma concentration-time profile from time zero to the time of the last quantifiable concentration (C_{last})
AUC_{inf}^*	ln	A, D	Area under the plasma concentration-time profile from time zero extrapolated to infinite time
$AUC_{inf,u}^*$	ln	A, D	Unbound area under the plasma concentration-time profile from time zero extrapolated to infinite time
C_{max}	ln	A, D	Maximum plasma concentration
$C_{max,u}$	ln	A, D	Unbound maximum plasma concentration
T_{max}	R	D	Time for C_{max}
$t_{1/2}^*$	R	D	Terminal half-life
CL/F^*	ln	A, D	Apparent clearance
CL_u/F^*	ln	A, D	Unbound apparent clearance
V_z/F^*	ln	A, D	Apparent volume of distribution
V_{z_u}/F^*	ln	A, D	Unbound apparent volume of distribution
Fu^+	R	D	Fraction unbound

Key: A=analyzed using statistical model, D=displayed with descriptive statistics,
ln=natural-log transformed, R=raw (untransformed), *=if data permits; u=unbound fraction
+ = Reported in eNCA as protein free fraction.

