8.2. Statistical Analyses of PK Parameters

One-way analysis of variance (ANOVA) will be used to compare the natural log transformed PF-05221304 AUC_{inf} , AUC_{last} and C_{max} , unbound AUC_{inf} ($AUC_{inf,u}$), unbound AUC_{last} ($AUC_{last,u}$), and unbound C_{max} ($C_{max,u}$), as data permit, for each of the hepatic impairment classification cohorts (Test) to the cohort without hepatic impairment (Reference). Estimates of the adjusted mean and corresponding 90% confidence intervals will be obtained from the model for each cohort. Estimates of the adjusted mean differences (Test-Reference) and corresponding 90% confidence intervals will be obtained from the model as well. The adjusted mean estimates and adjusted mean differences and 90% confidence intervals for the estimates and differences will be exponentiated to provide estimates of adjusted geometric means and estimates of the ratio of adjusted geometric means (Test/Reference) and 90% confidence intervals for the estimates and for the ratios respectively (see Appendix 1 for SAS code).

Additionally, as an exploratory analysis, age, body weight, and gender (see Section 6.4) will be explored as a covariate/factor in the ANOVA/ANCOVA model, as appropriate (see Appendix 1 for SAS code).

Linear regression may be used to analyze the potential relationship between the following PK parameters -AUC_{inf}, and CL/F separately - and the following hepatic function - serum albumin, prothrombin time, and total bilirubin separately -. Estimates of the slope and intercept, together with their precision (90% confidence interval [CI]), and the coefficient of determination (ie R-squared and adj-R-squared) will be obtained from the model.

Plots of PK parameters -AUC_{inf}, and CL/F separately - versus hepatic function - serum albumin, prothrombin time, total bilirubin separately - will be constructed. A regression line and 90% confidence region for the PK parameters and hepatic function will be included. (See appendix 1 for example of SAS code to produce the figure).

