Residuals from the models will be examined for normality and the presence of outliers via visual inspection of plots of residuals vs predicted values and normal probability plots of residuals but these will not be included in the clinical study report. If there are major deviations from normality or outliers then the effect of these on the conclusions will be investigated through alternative transformations and/or analyses excluding outliers. Alternative model structure may also be considered. Justification for any alternative to the planned analysis will be given in the report of the study.

The following PK parameters will be summarized by hepatic function Cohort:

Table 4. PK Parameters to be Summarized Descriptively by Cohort	
Parameter	Summary Statistics
C _{max} , AUC _{last} , AUC _{inf} , CL/F, V _z /F, AUC _{inf,u} , AUC _{last,u} , C _{max,u} , CL _u /F, and V _{zu} /F	N, arithmetic mean, median, cv%, standard deviation, minimum, maximum, geometric mean and geometric cv%.
T _{max}	N, median, minimum, maximum.
t _{1/2, fu}	N, arithmetic mean, median, cv%, standard deviation, minimum, maximum.

Box and whisker plots for PF-05221304 AUC_{inf}, AUC_{last}, C_{max}, AUC_{inf,u}, AUC_{last,u}, and C_{max,u} individual subject parameters will be plotted by hepatic function cohort and overlaid with geometric means.

Supporting data from the estimation of t^{1/2} and AUC_{inf} will be listed by cohort: terminal phase rate constant (k_{e1}); goodness of fit statistic from the log-linear regression (r²); the percent of AUC_{inf} based on extrapolation (AUC_{extrap}%); and the first, last, and number of time points used in the estimation of k_{e1}. This data may be included in the clinical study report.

Presentations for PF-05221304 concentrations will include:

- a listing of all concentrations sorted by hepatic function cohort (present in heading), subject id and nominal time postdose. The concentration listing will also include the actual times. Deviations from the nominal time will be given in a separate listing.
- a summary of concentrations by hepatic function cohort and nominal time postdose, where the set of statistics will include n, mean, median, standard deviation, coefficient of variation (cv), minimum, maximum and the number of concentrations above the lower limit of quantification.

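### Fraction unbound (f_u) is the only one of five primary endpoints with no directly reported Test/Reference ratio, 90% CI or by-cohort plot; the loss is small and the remedy nearly free

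*SAP*

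**What the plan says.** The primary objective in protocol section 2 opens "To compare the pharmacokinetics of PF-05221304 (both total and unbound) following administration of a single oral dose", and f_u is one of its five primary endpoints. Protocol 1.3.2 gives f_u a purpose of its own in the sentence that begins "To assess the in vivo protein binding of PF-05221304 with varying degrees of hepatic impairment, the fraction unbound". Protocol 9.3.2 says that f_u "will be determined and reported for each subject by the analytical lab", and its Table 5 defines each unbound exposure as f_u times the total exposure.

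The analysis text treats f_u differently from the other four primary endpoints:

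- **ANOVA.** SAP 8.2 says "One-way analysis of variance (ANOVA) will be used to compare the natural log transformed PF-05221304" and names AUCinf, AUClast, Cmax, AUCinf,u, AUClast,u and Cmax,u. Protocol 9.3.3 names the same six.
- **Descriptive summary.** Protocol 9.3.3 includes f_u among the parameters that "will be summarized descriptively by hepatic function cohort".
- **SAP Table 3.** The key reads "A=analyzed using statistical model, D=displayed with descriptive statistics". The f_u row carries R (raw scale) and D, without A.
- **SAP Table 4.** f_u gets N, arithmetic mean, median, CV%, SD, minimum and maximum, with no geometric mean or geometric CV%.
- **Plots.** In SAP 8.2 the "individual subject parameters will be plotted by hepatic function cohort and overlaid with geometric means", and the parameters named are the six ANOVA parameters. The by-cohort plots in protocol 9.3.3 name the same six.

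**The concern.** The opening of protocol 9.3.3 and SAP 8.1 both say, of PK parameters in general, that 90% CIs on the Test-Reference difference are how the effect of impairment will be assessed. The specific lists carry this through for four of the five primary endpoints. As written, the report would print a ratio and interval for secondary AUClast and AUClast,u but none for primary f_u.

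On the log scale, ln(AUCinf,u) = ln(f_u) + ln(AUCinf). The f_u ratio therefore shows how much of a change in unbound exposure comes from altered binding and how much from altered total exposure. At stake is whether the reader is given that interval directly or has to reconstruct it.

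**Working it through.** **1. The five primary endpoints side by side**

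| Endpoint | ANOVA list (protocol 9.3.3, SAP 8.2) | SAP Table 3 | Geometric statistics, SAP Table 4 | By-cohort plot |
|---|---|---|---|---|
| Cmax | yes | ln; A, D | yes | yes |
| AUCinf | yes | ln; A, D | yes | yes |
| Cmax,u | yes | ln; A, D | yes | yes |
| AUCinf,u | yes | ln; A, D | yes | yes |
| f_u | no | R; D | no | no |

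Of the eight secondary PK parameters, Table 3 codes six as A: AUClast, AUClast,u, CL/F, CLu/F, Vz/F and Vzu/F. Only AUClast and AUClast,u are in the SAP 8.2 ANOVA list, so by the operative list 2 of 8 receive ANOVA.

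**2. The plan's own precision figure**

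Protocol Table 4 concerns AUCinf, with 6 per cohort and 80% tolerance probability. It reproduces with two cohorts of 6 (10 df):

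half-width = t(0.95, 10) × SD × √(2/6) × √(χ²(0.80, 10)/10) = 1.812 × 0.5774 × 1.159 × SD = 1.213 × SD.

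- SD 0.16: 0.194, so 2·exp(∓0.194) = 1.65 to 2.43.
- SD 0.23: 0.279, so 1.51 to 2.64.
- SD 0.28: 0.340, so 1.42 to 2.81.

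All three match. The documents give no SD for ln(f_u), so 0.10, 0.20 and 0.30 are assumed below.

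**3. The point ratio is already in the planned output**

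Since Cmax,u = f_u × Cmax, the difference in mean ln(f_u) is the difference in mean ln(Cmax,u) minus the difference in mean ln(Cmax). Hence GMR(f_u) = GMR(Cmax,u)/GMR(Cmax), exactly, when the same subjects contribute. AUCinf,u/AUCinf works in the same way, where AUCinf can be derived. In one simulated four-cohort data set the direct and derived ratios agreed for all three comparisons (1.472, 1.446 and 2.231).

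The interval does not follow from those two ratios alone. With an SD of 0.28 for both ln(AUCinf) and ln(AUCinf,u), the SD of ln(f_u) runs from 0.396 (correlation 0) to 0.089 (correlation 0.95), and the CI factor from 1.48 to 1.09. The f_u SD in SAP Table 4 supplies what is missing.

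**4. Rebuilding the 90% CI**

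- *Raw scale.* N, mean and SD per cohort give the pooled variance, so the ANOVA difference and its CI are recovered exactly apart from rounding. In one simulated data set both routes gave 0.00119 to 0.00647.
- *Log scale.* Take the exact ratio from step 3 and approximate each cohort's SD by SD_ln = √(ln(1 + CV²)). Pool over the four cohorts and use half-width = t(0.95, df) × pooled SD × √(1/n_ref + 1/n_test).

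Median error of the worse limit in simulated trials:

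| Assumed SD of ln(f_u) | 0.10 | 0.20 | 0.30 |
|---|---|---|---|
| 6 per cohort | 0.12% | 0.48% | 1.17% |
| Severe vs Normal, Cohort 4 = 4 | 0.13% | 0.55% | about 1.3% |

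A cruder rebuild ignores the exact ratio and also takes the log mean from the arithmetic mean, as ln(mean) − SD_ln²/2. With 6 per cohort its medians are 0.18%, 0.73% and 1.75%, and its 95th percentiles 0.51%, 2.06% and 4.81%. With mean and SD rounded to 3 significant figures (assumed), the medians become 0.36%, 0.84% and 1.83%.

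**5. The interval the fix would report**

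exp(t(0.95, df) × SD × √(1/n_ref + 1/n_test)) at SD 0.10, 0.20 and 0.30:

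- 6 per cohort (df 20; 1.7247 × 0.5774 = 0.996): 1.105, 1.220, 1.348.
- Severe vs Normal, Cohort 4 = 4 (df 18; 1.7341 × 0.6455 = 1.119): 1.118, 1.251, 1.399.
- Cohort 1 = 10 (df 24; 1.7109 × 0.5164 = 0.883): 1.092, 1.193, 1.303.

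These factors are the expected width of the added interval. They do not measure an error in the plan.

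**The case against.** The strongest reply is that this is a deliberate and consistent choice. Protocol 9.3.3 and SAP Tables 3 and 4 all place f_u in the descriptive set. Summaries by cohort, read side by side, are a form of comparison. SAP 4.1 and 4.2 plan no hypothesis test and no decision rule, and nothing in the readable text requires a model-based interval for every primary endpoint. f_u also already enters AUCinf,u and Cmax,u, which have intervals.

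All of that stands, and it limits the point to reporting. It does not remove it. An interval for unbound exposure is not an interval for binding. In a study whose output is estimates and intervals, it is reasonable for the sponsor to print the one belonging to a named primary endpoint.

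A reader might infer more than the documents support:

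- *That the plan contradicts itself.* It does not. The general sentences about PK parameters are narrowed by explicit lists and by the Table 3 coding, and these agree on f_u.
- *That the comparison is lost.* It is not. The ratio is exactly recoverable and the interval closely so.
- *That most secondary parameters are better served than f_u.* Table 3 suggests this with six coded A, but the SAP 8.2 list gives ANOVA to only two of the eight.
- *That no f_u model exists anywhere.* Redactions in protocol 9.3.3, SAP 8.1 and SAP Appendix 1 prevent certainty. The readable f_u row in Table 3, without A, makes a hidden model unlikely.

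**Conclusion.** The point holds as a minor, optional improvement. In the readable text, f_u is the one primary endpoint of five without a directly reported Test/Reference ratio and 90% CI and without a by-cohort plot.

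What is missing is the printed interval, the geometric statistics and the plot. The underlying information is not lost. Exact recovery of the ratio assumes that the same subjects contribute to the total and unbound parameter. The error figures for the interval assume log-normal f_u, ln-scale SDs of 0.10 to 0.30, and the cohort sizes shown. No conclusion, error rate or sample size changes.

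**What to change.** Four edits would close the gap:

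- Add ln(f_u) to the one-way ANOVA lists in protocol 9.3.3 and SAP 8.2, with Test/Reference geometric mean ratios and 90% CIs.
- Recode f_u in SAP Table 3 as ln; A, D.
- Add geometric mean and geometric CV% for f_u in SAP Table 4.
- Add f_u to the by-cohort plots in both documents.

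The analysis cost is one more variable through the PROC GLM code in SAP Appendix 1, using values already reported for each subject. No further samples or subjects are needed. The protocol wording needs an edit. Protocol section 9 says that "any major modifications of the primary endpoint definitions or their analyses will also be reflected in a protocol amendment", so an amendment is needed only if the sponsor counts this as a major modification.

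### The SAP contradicts itself on whether clearance and volume get Test/Reference ratios, and plans no estimate of change for half-life, which the secondary objective sets out to compare (minor)

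*SAP*

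**What the plan says.** **Objective.** Protocol section 2 sets a secondary objective, "To compare additional pharmacokinetic parameters (both total and unbound) of PF-05221304 following administration of a single oral dose", with impaired cohorts judged against the matched reference. Its endpoints include CL/F, CLu/F, Vz/F, Vz,u/F and t1/2, qualified by "as data permit".

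**Reason for the long sampling.** Protocol 1.3.2 says that "the PK sampling will be collected serially up to 144 hours post-dose", because half-life may be longer in the impaired cohorts.

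**Model list.** SAP 8.2: "One-way analysis of variance (ANOVA) will be used to compare the natural log transformed PF-05221304" AUCinf, AUClast, Cmax and the unbound version of each. Protocol 9.3.3 has the same six and names the remaining parameters only for descriptive summary.

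**Parameter table.** The footnote to SAP Table 3 reads "Key: A=analyzed using statistical model, D=displayed with descriptive statistics". The Vz/F row reads "ln A, D Apparent volume of distribution" and the Vz,u/F row "ln A, D Unbound apparent volume of distribution"; CL/F and CLu/F carry the same codes. The half-life row reads "R D Terminal half-life", that is, untransformed and descriptive.

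**Descriptive table.** SAP Table 4 gives N, geometric mean and geometric CV (among others) for clearances and volumes, but only arithmetic statistics, median and range for t1/2.

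**General statement.** SAP 8.1 plans ANOVA-based 90% CIs for PK parameters without saying which.

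**The concern.** A programmer working from Table 3 would fit ten parameters; one working from 8.2 would fit six. For the four in dispute, the report could contain ratios with CIs or none, and both would follow the SAP.

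Half-life is a separate matter. It is a named endpoint of an objective to compare, and sampling to 144 hours is justified by its possible prolongation, yet its only planned output is a set of cohort summaries on the raw scale. The AUCinf ratio settles CL/F. It does not show whether volume changed too, and half-life depends on both. Protocol 1.4 says the data are to support dosing recommendations, and half-life bears on time to steady state and accumulation, so an estimate of its change with an interval would be useful.

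**Working it through.** **1. Lists side by side.**

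| Parameter | SAP Table 3 | SAP 8.2 ANOVA list | SAP Table 4 |
|---|---|---|---|
| CL/F, CLu/F | ln; A, D | absent | geometric mean and CV |
| Vz/F, Vz,u/F | ln; A, D | absent | geometric mean and CV |
| t1/2 | R; D | absent | arithmetic only |

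Four parameters conflict; t1/2 does not. Of the four, only CL/F is in another readable model, the optional regression on hepatic function.

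**2. Which contrasts the ANOVA already contains.** Protocol Table 5 sets CL/F = Dose/AUCinf. With one fixed dose, ln CL/F = constant − ln AUCinf, so the CL/F ratio and CI are the reciprocals of those for AUCinf.

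This does not carry over to unbound clearance:
- Table 5 sets AUCinf,u = fu × AUCinf, so Dose/AUCinf,u = (CL/F)/fu.
- Table 5 also sets CLu/F = fu × CL/F.
- The two differ by fu², so their Test/Reference ratios differ by the square of the fu ratio.
- Vz,u/F = fu × Vz/F has the same defect.

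**3. What the descriptive output allows.** For Vz/F, cohort variance on the ln scale is ln(1 + gCV²). Pool over cohorts to s²; the interval is the ratio of geometric means × exp(±t(0.95, 20) × √(s²(1/6 + 1/6))). On simulated data for four cohorts of six, this gave 0.826 (0.588 to 1.161), identical to the ANOVA.

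For half-life, ln t1/2 = constant + ln Vz/F + ln AUCinf. The ratio follows: 0.826 × 1.604 = 1.325 on the same data, matching the direct calculation. The CI does not follow, because its variance needs the covariance of ln Vz/F and ln AUCinf, which is not among the planned summaries.

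**4. The plan's own precision figure.** Protocol Table 4 is reproduced by 2 × exp(±h), h = t(0.95, 10) × SD × √(1/6 + 1/6) × √(χ²(0.80, 10)/10):

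| SD (ln) | Computed | Stated |
|---|---|---|
| 0.16 | 1.647 to 2.428 | 1.65; 2.43 |
| 0.23 | 1.513 to 2.644 | 1.51; 2.64 |
| 0.28 | 1.424 to 2.809 | 1.42; 2.81 |

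These SDs are for AUCinf. None is given for t1/2 or Vz/F.

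**5. Precision if t1/2 and Vz/F are modelled.** Pooled ANOVA, without the tolerance factor: factor = exp(t(0.95, df) × SD × √(1/n₁ + 1/6)), df = 20 for 6 v 6, and 18 if the severe cohort has 4.

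| Assumed SD (ln) | 6 v 6 | 4 v 6 |
|---|---|---|
| 0.16 | ×/÷ 1.173 | ×/÷ 1.196 |
| 0.23 | ×/÷ 1.257 | ×/÷ 1.294 |
| 0.28 | ×/÷ 1.322 | ×/÷ 1.368 |
| 0.35 | ×/÷ 1.417 | not computed |
| 0.40 | ×/÷ 1.489 | ×/÷ 1.565 |
| 0.50 | ×/÷ 1.645 | ×/÷ 1.750 |

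With 6 v 6, an observed 1.3-fold half-life difference would exclude no change at SD 0.23 (1.3/1.257 = 1.03) but not at 0.28 (1.3/1.322 = 0.98).

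**The case against.** The best defence is that a descriptive secondary comparison is legitimate. The SAP plans no hypotheses and no decision rules, the endpoints are conditional on the data, and Tmax, under the same objective, is also only summarised. Average exposure at steady state under linear kinetics depends on CL/F, which the AUCinf ratio covers, and Protocol 1.3.2 regards single-dose PK as generally predictive of exposure on repeated dosing. This stands, and it is why the half-life part is an improvable choice and not an error.

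Three stronger readings are tempting, and the documents do not support them:

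- *That no ratio or CI is planned for the volumes.* Table 3 says they are modelled, SAP 8.1 is unrestricted, and the Appendix 1 code takes any ln-transformed variable. The plan is undetermined here, not silent, and for Vz/F the interval can be rebuilt from Table 4.
- *That Table 3 and 8.2 also conflict on half-life.* They agree, as do SAP Table 4 and Protocol 9.3.3.
- *That CLu/F is already covered as the reciprocal of AUCinf,u.* Under Protocol Table 5 as written it is not.

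Nor is the absence of Vz/F from the SAP regression a defect. Protocol 9.3.3 offers that regression as optional, with Vz/F as an example, and Protocol section 9 lets the SAP modify the methods.

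The defence does not answer the disagreement between Table 3 and 8.2. It also leaves the fact that SAP 8.1 makes the 90% CI the study's way of expressing an effect, which half-life does not receive.

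**Conclusion.** The point holds at minor severity. The internal conflict over CL/F, CLu/F, Vz/F and Vz,u/F is certain from the text. It costs nothing for CL/F, whose ratio follows from AUCinf. For half-life, the readable plan gives no estimate of change and no interval, and a geometric-ratio CI cannot be recovered from the planned summaries, although a raw-scale difference and CI could be computed from N, mean and SD.

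The primary exposure ratios are unaffected, so a reader should not infer that the study's main conclusion is at risk. The precision figures rest on assumed SDs: 0.16 to 0.28 borrowed from AUCinf, and 0.35 to 0.50 added as a range. Parts of SAP 8.1, Appendix 1 and Protocol 9.3.3 are redacted, so the conclusion is limited to the readable text.

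**What to change.** 1. In SAP 8.2, add ln t1/2 and ln Vz/F to the ANOVA list, with geometric-mean ratios and 90% CIs, as data permit.
2. In SAP Table 3, recode t1/2 as ln; A, D. In SAP Table 4, add its geometric mean and geometric CV.
3. State in the SAP that, at one fixed dose, the CL/F ratio is the reciprocal of the AUCinf ratio, so no separate model is needed.
4. Reconcile Protocol Table 5, where multiplying CL/F and Vz/F by fu is inconsistent with AUCinf,u = fu × AUCinf. Until then, do not model CLu/F or Vz,u/F, claim no reciprocal relation for CLu/F, and mark both as pending in Table 3.

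If the sponsor prefers a descriptive comparison, the minimum is to change A, D to D for the four parameters and say openly that this secondary comparison is descriptive.

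The cost is two more runs of the Appendix 1 ANOVA code, a few table rows, and a short SAP amendment before database release. Protocol 9.3.3 can be aligned at the same time. No further subjects, samples or assays are needed.
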